6. POTENTIAL RISKS

Staff level:

Staff members could feel pressure to participate in the study. It will be made clear, through written materials and oral instruction, that staff participation in the project's evaluation is completely voluntary. The cost and implementation analyses and their purpose in understanding the feasibility of implementing A-CHESS will be explained. Staff responses to interviews will be

coded and responses will be accessible only by evaluation team members (survey and interview data will not be accessible to other clinic staff members, including the A-CHESS Site Coordinator). If staff members are asked to complete the interview or survey, but refuse, the A-CHESS Site Coordinator will attempt to identify replacement staff respondents. In addition, members of management and clinical supervision will be notified of the importance of staff not feeling coerced to participate the study, A-CHESS recruitment, or survey completion.

The potential risk for staff is that the information they provide could be offensive to members of management or their peers. Hence, protecting staff confidentiality is an important element of our protection plan. Researchers ([name], [name]) trained in protecting consumer confidentiality will conduct interviews. Data collected in the interviews and surveys will have a code number assigned (as previously defined) attached prior to storing in the project dataset. In this way, we can ensure that the interviewer (in the case of interviews) and the University of Wisconsin database administrator (in the case of surveys) will be the only person who can identify the interviewee's responses. Also, managers or other members of the organization will not see transcripts of interviews.

Consumer level:

There is a risk that patient subjects may feel uncomfortable sharing personal information or answering weekly survey questions through A-CHESS or questions about COVID-19 on the supplemental survey and in-depth interviews, especially about sensitive topics. Participants will be asked personal questions related to past behaviors and experiences, such as illicit drug use, that could produce psychological stress.

The on-line consent process will inform consumers of the need to provide the A-CHESS app with information on an ongoing basis to determine whether treatment goals are being met. Consumers must agree to allow monitoring of their A-CHESS usage. We will ask consumers to consent to share information with their SUD provider. Consent to share information will also be provided through the consent form and will comply with 42CFR regulations, specifying what information will be shared with the SUD provider and how long the information will be shared. The consumer will be given the right not to share specific information with specific people and retain the right to revoke the permission granted at any point. Informed consent and assurance of confidentiality, with a description of privacy protection measures, should assist with lowering participant anxiety.

An additional and similar consent process will be used for the COVID-19 supplemental patient survey and in-depth interviews. Individual survey and in-depth interview results will not be shared with anyone outside the research team, including with counselors or others at the treatment organization.

Consumers can turn on must consent GPS monitoring of their location via A-CHESS, which could pose a privacy risk. GPS monitoring is included in A-CHESS to trigger a system response when consumers approach high-risk locations. These locations are identified and entered by the consumer. GPS monitoring will be used for no other purpose than avoidance of high-risk locations. The GPS data is strictly a feature of the A-CHESS app and will not be used for any type of analysis as part of this study. Users are able to turn the GPS monitoring on or off (and similarly can choose whether or not to participate in other aspects of A-CHESS such as the

discussion group). The COVID-19 surveys do not involve GPS monitoring, but the patient survey will ask about patients' zipcode to help understand their COVID-19 risk and community spread. All protected health information will be stored securely and only with a unique study ID number (not the patient's name).

There is also a risk of breach of confidentiality. Dissemination of some of the more sensitive information could result in risk to reputation. To mitigate the risk of consumer breaches of confidentiality, all subjects will be assigned a code number. A list of subject code numbers will be maintained by the project director ([name]) and stored in a password-protected spreadsheet.

There is a risk that information and resources consumers may divulge in A-CHESS will be used to the detriment of the subjects. Particular sources of risk include A-CHESS communications written within the discussion groups or personal profiles. Consumers will be instructed not to use their real names as a code name and will be warned of the potential dangers of divulging confidential information (e.g., real names or telephone numbers). An explicit statement regarding security and lack of confidentiality will be provided each time users enter discussion groups. These data will be collected by subjects' codename and will not be attached to real names or identities.

Additionally, numerous methods are taken to assure the security of A-CHESS data, COVID-19 survey data, and patient in-depth interview recordings and transcriptions. The data from various components of A-CHESS will be housed on the secure CHESS servers at the University of Wisconsin. A database administrator ([name]) will be the only member of the evaluation team who will have direct access to this database. The CHESS Center, [name], and [name] have extensive experience with HIPAA and IRB compliant practices for accessing, storing, and using personal health information. Furthermore, the A-CHESS registry is equipped with a log that records who accessed what data, at what time, and for how long as an added layer of security. Consumer data will be identified using a unique A-CHESS ID number (based on the A-CHESS log-in). Similarly, survey and in-depth interview data will be stored securely as indicated above.

In summary, during the on-line consent, potential subjects will be informed of (1) the nature and purpose of the study, (2) the types of data that will be collected from smart phone use tracking, (3) measures taken to insure the confidentiality of data collected (4) their right to leave the study at any time, and (5) the timeline of the study. Consent will be documented by obtaining online IRB-approved consent forms containing all of the above information. Consent forms will be digitally based. The A-CHESS system will store the consent form at the University Wisconsin – Madison on a secure server. The consumer can download a PDF of the consent form. Upon signing the consent forms, the A-CHESS Site will provide a unique login name for the system, a mandatory requirement of HIPAA. A similar online consent will be provided to participants invited to complete the COVID-19 patient survey. Verbal consent with a trained research assistant will be used for in-depth interviews related to COVID-19. Copies of all consents will be provided to participants and stored securely.

A Certificate of Confidentiality has automatically been granted by virtue of this study being funded through the National Institutes of Health. This provides an additional level of protection for participant data.

There is a risk that inaccurate or harmful information could be provided to consumers; to

mitigate this risk, all A-CHESS content has been screened by experts from our A-CHESS Consumer Advisory Committee, which has existed at the Center for 7 years. Despite the rigorous review process that occurs with all CHESS content, we will encourage study participants during training to contact their counselor or A-CHESS Site Coordinator if they are uncomfortable with the information provided by A-CHESS.

Features such as a “panic button” could produce over-reliance on a system such as A-CHESS to provide support during periods of intense craving and when the perceived risk for relapse is high. We don’t expect that such incidences would be frequent. It is possible that a counselor and peers may not be immediately available to answer a call for help from an A-CHESS user. Study participants will be told that every effort will be made for their pre-designated support team to follow-up on their call for help. Additionally, if nobody in their immediate support network is able to respond, the individual calling for help will be forwarded to the central desk of their treatment agency and referred to other support people as needed. Study participants will be told during training that the panic button is for the most serious situations where relapse is imminent, and not to be used when other modes of communication (e.g., phone call, text message) will suffice.

Study data collected at both the staff and consumer levels will be input to a SQL Server database housed at CHESS for analysis purposes. The University of Wisconsin database administrator will manage access to appropriate levels of study data for the evaluation team via password-protected accounts.

7. MEASUREMENT OF EFFECT

All scales used in this study have good psychometric properties with similar populations. Listed below are the factors to be measured and measurement instruments with references to validation studies.

Descriptive Statistics - Organizational traits such as admission and rural v. urban will be obtained via IDPH data at four points during the study (N-SSATS⁵⁵). Patient traits such as age, gender, ethnicity, and poverty level will also be obtained at four points during the study via IDPH data (TEDS⁵⁶). Counselor traits such as gender, ethnicity, race, and certification or education level will be obtained via the organizational survey.

REACH - The percentage of patients that download the A-CHESS app and frequency of use in days will be obtained monthly during the study via the A-CHESS server and IDPH data.⁵⁰

Adoption - The percentage of counselors using A-CHESS will be assessed via the organizational survey and A-CHESS logs.⁵⁹

Effectiveness - Retention (length of stay) will be assessed using IDPH data.⁶¹

Maintenance - The organizational survey, which will be administered at two points during the study, will assess Financial Resource Availability.⁶² The staff survey will assess A-CHESS Implementation Fidelity (developed for trial) and Organizational Change Manager (OCM)⁶³. The OCM and A-CHESS Implementation Fidelity will be administered at two points during the study.

Patient COVID-19 Surveys – Surveys will assess how A-CHESS use may have lessened the impact of COVID-19 on anxiety and loneliness. We will collect several patient socio-

demographic traits as recommended by NIH, including age, race, self-identified gender, sex at birth, approximate income level, educational attainment, sexual orientation, marital status, housing type, family size, health insurance. We will use several validated measures to assess patients' substance use severity, loneliness, anxiety, and substance use disorder recovery strengths. Where validated measures are not available due to the rapidly emerging COVID-19 situation, we have drawn measures from existing population-based studies recommended by the National Institutes of Health.

8. STUDY PARAMETERS

The 16 participating Iowa SUD organizations will be assigned to the

- Control arm (typical Product Training/On-line Support alone, n=8 organizations, n=20 sites) or
- Treatment arm (NIATx-TI framework plus Product Training/On-line Support, n=8 organizations, n=20 sites)

We will use a stratified randomization (or blocking with matched pairs). The matching criteria, using organizational characteristics and technology adoption traits, are:

- a) Innovation score per organization
- b) # of rural sites (due to the digital divide in these areas)
- c) # of outpatient sites per organization.

The innovation score per organization will be calculated based on the level of "success" (i.e. volume of patient enrollment) the organization had with implementing an online gambling portal in 2014. The implementation of the online gambling portal was in partnership with the Iowa Department of Public Health, who will provide gambling project enrollment numbers. This is an objective and relevant measure for innovativeness of the organizations as we will be implementing a mobile technology that will require the organizations to disperse the technology to their patients.

We will apply urn randomization to achieve arm balance, using these 3 traits (e.g., # above/below mean for each trait or # of outpatient sites). An organization from each matched pair will be assigned to a study arm. Organizations (and their staff and patients) will have access to A-CHESS for the duration of the study regardless of which arm they are randomized to. Organizations and staff in the treatment arm will have access to NIATx-TI for 36 months.

9. STATISTICAL CONSIDERATIONS

Sample Size, Power & Data Analysis Plan: We will fit a mixed-effects model with the appropriate link function (e.g., linear, log) to the monthly results for the performance measures, % of eligible A-CHESS users and frequency of A-CHESS use, for each of the participating organizational sites, clustered by organization, and estimate the NIATx-TI framework and

product training effects. A mixed-effect model offers 2 advantages over conventional regression models: 1) The mean outcomes for a given treatment organization are expected to be correlated from month to month. A mixed-effect model allows for auto-correlated error terms. 2) Many unobservable treatment organizational site characteristics are likely to influence the key measures. Random effects at the treatment organization site level can be employed within the mixed-effect model to capture the correlation introduced by such characteristics. Proper reflection of auto-correlation and random effects allows for more reliable estimates of the fixed effects, starting at baseline, then again during the 18-month test and post-test periods. The power of the study design is determined by the anticipated standardized effect size based on effects experienced in the IRHIT project. The standardized effect size is calculated following Cohen's definition of mean effect size divided by effect size standard error.⁶⁵ The higher the standardized effect size, the more powerful the study design. Historically, cluster-randomized trials portray the standardized effect sizes of 0.2, 0.5 and 0.8 as small, medium, and large respectively. The IRHIT pilot data found that NIATx-TI increased client technology use rates by 12.4% (increase of intervention success), which can be transformed into Cohen's $d = 0.352$.⁶⁶ Intraclass correlation (ICC) among sites affects the power of cluster-randomized trials.⁶⁷ An estimate of ICC is around 0.10.⁵⁰ With a total of 8 organizations, with 20 organizational sites in each arm, where each site has an average 62 eligible patients, the study will achieve a power of .90 with a type I error rate of 0.05.

Mediational (and Maintenance) analysis: We will examine the mediating effects of organizational factors of: % of counselors using A-CHESS, organizational readiness (via OCM), financial resource availability (via Klein's inventory), and A-CHESS implementation readiness on A-CHESS use through a causal mediational analysis, using data from end of intervention periods. These factors will be analyzed using mixed-effects models. Through a mediation analysis,^{68,69} we can estimate the direct (A-CHESS use with NIATx TI and Product Training) and indirect effects (Adoption and Implementation factors) of each implementation arm on A-CHESS use. We will test the mediation effect of each potential mediator at each time point as well as across time. The R package 'mediation,' will estimate the causal mediation effects, examine moderated mediation effects, and conduct sensitivity analysis.⁷⁰

Effectiveness analysis: We will compare a retention rates in the 2 different arms using hierarchical linear models, where arm membership is used as the treatment assignment. We will examine the distribution of this outcome measure and will implement an appropriate transformation or nonlinear link function when appropriate (e.g., logistic, Poisson, exponential). Monthly data collection of the Effectiveness as well as Reach (A-CHESS Use) measures, allows for analysis after each stage of NIATx-TI.

Qualitative Analysis: The qualitative portion of the study will support the specific aims by exploring how NIATx-TI and product training are implemented, how implementation affects A-CHESS use, and how staff users react to NIATx-TI, product training, and A-CHESS. *During the study*, interviews with a randomly selected site in all organizations $n=16$ will occur at Ms 26-30 (at the end of intervention phase) and 44-48 (at the end of sustainability phase), with the same sites in each phase, to gain a retrospective understanding of what occurred during implementation. The interviews will include closed and open-ended questions designed to explore participants' experiences within each arm and the perceived effectiveness of each approach in assisting with implementing A-CHESS. The closed-ended questions will be based on elements of CFIR, developed by Damschroder et al. (2013),⁷¹ that will address: 1) intervention characteristics; 2) outer setting; 3) inner setting; and 4) process. The additional open-ended questions will allow for discovery of other factors affecting NIATx-TI, product training, and A-CHESS implementation. The information collected will inform our understanding

of implementation assets, barriers, and potential revisions for each approach. Interviews of up to 30 minutes will be conducted with the organization's Executive Director, the site's clinical director, the A-CHESS site coordinator, and a randomly selected full-time site counselor. Four interviews/organization will result in n=64 interviews per phase and up to n=80 interviews overall (assuming 25% turnover between phases).

The qualitative analysis will be conducted by a team consisting of a qualitative methodologist ([name]), an outreach specialist from the Iowa Consortium for Substance Abuse Research and Evaluation, and Project Director from NIATx/CHESS. [name] will train the research team to assure that proper and consistent interviewing and analysis techniques are used. All interviews will be audio recorded and transcribed verbatim. Using a coding scheme derived from CFIR concepts, project staff will conduct a directed content analysis⁷¹ of these data. To assure coding consistency, every fourth interview will be double-coded. Significant inconsistencies will be discussed within the team and recoded. In addition, an inductive approach based on grounded theory and dimensional analysis⁷²⁻⁷⁴ will be used to identify and explore additional contextual and process factors that affect NIATx-TI and product training, as well as A-CHESS use. The inductive analysis will emphasize open and axial coding; coding divergences will provide opportunities for further reflection and exploration during team analysis meetings. Both directed and inductive analyses will include within-site, cross-site, and cross organization comparisons. Qualitative analysis will begin with the first interview and will continue in tandem with data collection, allowing the investigators to use later interviews to delve into factors that are identified in early interviews.

The qualitative analysis will produce a description of the technology implementation process. It will encompass grounded explications of the theoretical concepts that influenced development of the NIATx-TI framework. This description will enhance our understanding of how the NIATx-TI framework works, promoting valuable insights that can be applied to future dissemination of mobile e-health applications.

Analysis of Supplemental COVID-19 Patient Survey and In-Depth Interview Data: Patient survey data will be matched with longitudinal app usage data. We anticipate using linear regression models to quantify the association between app usage (modeled continuously and binary as an indicator of meaningful use of A-CHESS) and several continuous outcomes based on validated measure – anxiety (PROMIS 29) and loneliness (UCLA Loneliness Scale-8). We will adjust for potentially confounding variables, including socio-demographic characteristics, recovery capital, criminal justice involvement, and substance use disorder severity. Further, we will use logistic or log-binomial regression models to assess how app usage is associated with substance use disorder treatment participation (e.g., AA/NA/self-help group participation, attendance at group therapy).

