Organizational Surveys: Will be completed by a member of the management team two times during the project (organizational baseline and end of the intervention.) To increase survey completion rates for the organizational surveys, we conduct follow-up phone calls and e-mails with the change leaders at Week 1 of post-survey distribution to assure the survey receipt, then at Weeks 4 and 12-post survey distribution if surveys are not complete.

Staff Surveys: The full organizational and staff surveys (A-CHESS Implementation Fidelity, Organizational Change Manager, and Financial Resource Availability) will be administered two times during the project organizational baseline and end of the intervention). A 'generic' version of the Organizational Change Manager (OCM) will be administered prior to training. This

version of the survey will include questions that focus on prior change projects or innovations in the organization. During the second administration the OCM (as part of the full Staff Survey, the OCM questions will focus on the planned implementation of the e-health app. Each survey (A-CHESS Implementation Fidelity, Organizational Change Manager and Financial Resource Availability) is expected to take approximately 15 minutes or less to complete. Up to seven staff including a clinical supervisor, an administrative staff person, and up to 5 randomly selected counselors and Peer Recovery Support Specialists will complete the staff surveys. Staff completing surveys will receive consent documents when they are sent the survey link.

Each organizational site will receive a \$1000 stipend once all organizational and staff surveys, have been completed.

The trial will use 4 cohorts that will have staggered starts in order to have sufficient training resources for the trial (Figure 2). Each cohort will have 2 matched pairs with a control and treatment site in each pair, resulting in 4 organizations per cohort and n=16 organizations total.

Figure 2

[figure not shown]

Table 1 - Measures, Sources, and Tool/Frequency

Measurement	Measure Source	Data Source/Frequency (for Cohort 1)
Descriptive Statistics		
Organizational traits: Admissions, Rural v. Urban	N-SSATS ⁵⁵	IDPH – Ms 11, 22,34, 46
Patient traits: Age, Gender, Ethnicity, and Poverty Level	TEDS ⁵⁶	IDPH – Ms 11, 22,34, 46
Counselor traits: Age, Gender, Ethnicity, Race, Certification or education level		Organizational Survey – Ms 12, 30
Reach		

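### The traits used to match and allocate the 16 organizations are absent from the Reach and retention models; if they predict uptake, an organization-level test is conservative and loses power

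*Combined protocol and SAP*

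**What the plan says.** **Design.** Section 8 (Study Parameters) states: "We will use a stratified randomization (or blocking with matched pairs"). The criteria are an innovation score, the number of rural sites and the number of outpatient sites. The score is each organization's patient enrollment in a 2014 online gambling portal, supplied by the state health department. The section continues: "We will apply urn randomization to achieve arm balance, using these 3 traits", and then "An organization from each matched pair will be assigned to a study arm". Section 5 (Treatment Plan, Data collection) adds four staggered cohorts: "Each cohort will have 2 matched pairs with a control and treatment site in each pair". That makes four organizations per cohort and 16 in all, so eight pairs.

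**Analysis.** Section 9 (Statistical Considerations) fits a mixed-effects model to monthly results "for each of the participating organizational sites, clustered by organization, and estimate the NIATx-TI framework" and product-training effects. It mentions auto-correlated errors and says: "Random effects at the treatment organization site level can be employed within the mixed-effect model". Retention is compared with "hierarchical linear models, where arm membership is used as the treatment assignment".

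Neither model names a pair, a cohort or any of the three traits. The Use data text in section 5 plans a preliminary comparison of baseline organizational characteristics between arms, which is a description and not an adjustment. The power statement in section 9 does not mention the pairing either.

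**The concern.** Allocating on a trait balances it across arms, so the true variance of the arm difference falls when the trait predicts the outcome. A model that omits the trait does not register that reduction. The variation between pairs stays in the error term, the standard error is too large, and the test rejects less often than its nominal level.

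Section 8 gives reasons to expect such prediction. It calls the portal enrollment score relevant because this trial also asks organizations to hand a technology to their patients, and it justifies the rural count by the digital divide. These are the plan's own candidate predictors of Reach, the primary outcome. With eight organizations per arm there is little precision to give away. If the choice is left open, it could also be made after the data have been seen.

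**Working it through.** **1. The plan's own power figure.** Inputs from section 9: d = 0.352, ICC 0.10 among sites, 20 sites per arm, 62 eligible patients per site, type I error 0.05 (two-sided assumed).

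- Design effect = 1 + (62 − 1) × 0.10 = 7.1.
- Effective n per arm = 20 × 62 / 7.1 = 174.6.
- Noncentrality = 0.352 × √(174.6/2) = 3.29, so power = 0.908 with a normal reference (0.893 with t on 38 df).

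The stated .90 is reproduced. It is an unmatched calculation with sites as the independent units.

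**2. Effect of omitting effective matching.** Let V be the variance of an organization mean and ρ the share common to pair-mates. The unadjusted analysis estimates the variance of the arm difference as about 2V/8; its true value is 2V(1 − ρ)/8. The standard error is therefore too large by about 1/√(1 − ρ): 1.12 at ρ = 0.2 and 1.41 at ρ = 0.5. The resulting type I error depends on ρ and not on V. The documents give no ρ, so a range is used.

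**3. Illustration of power.** Assumption: ICC 0.10 split equally between organization and site, 2.5 sites per organization (20/8) and 155 patients per organization (2.5 × 62).

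- V = 0.05 + 0.05/2.5 + 0.90/155 = 0.0758.
- Paired test: noncentral t on 7 df with noncentrality 0.352/√(2V(1 − ρ)/8), which is 2.557 at ρ = 0.
- Trait-adjusted test: 16 organizations minus intercept, arm and one covariate = 13 df, with one trait assumed to carry all the shared variance.

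| Shared variance ρ | Unadjusted type I error (14 df) | Unadjusted power | Paired power (7 df) | Trait-adjusted power (13 df) |
|---|---|---|---|---|
| 0 | 0.050 | 0.66 | 0.60 | 0.65 |
| 10% | 0.041 | 0.67 | 0.64 | 0.70 |
| 20% | 0.031 | 0.68 | 0.69 | 0.75 |
| 30% | 0.023 | 0.69 | 0.75 | 0.80 |
| 50% | 0.010 | 0.71 | 0.87 | 0.91 |

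The unadjusted and trait-adjusted columns come from simulated trials of eight pairs. The paired and trait-adjusted tests both hold 0.05.

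**4. Why a pair term is not the first choice.** Pair effects cut the degrees of freedom from 14 to 7. Confidence intervals break even at ρ = 1 − (2.145/2.365)² = 0.177, so below about 18% shared variance pairing costs more than it gains. A random pair intercept limits that cost but brings another. With the pair variance truncated at zero and the df switching between 7 and 14, simulated type I error was 0.065, 0.057 and 0.051 at ρ = 0, 0.2 and 0.5. With a normal reference it was about 0.09 to 0.10.

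**5. Sensitivity to where the ICC sits.** Unadjusted against paired power:

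- With site as the only level of clustering: 0.87 v 0.84 at ρ = 0.1, 0.89 v 0.88 at 0.2, 0.90 v 0.92 at 0.3 and 0.92 v 0.98 at 0.5.
- With ICC 0.10 placed at organization level: 0.52 v 0.46 at ρ = 0, 0.52 v 0.55 at 0.2 and 0.54 v 0.75 at 0.5.

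**The case against.** A reader might infer that the planned test is simply too conservative. The documents do not support that, for three reasons.

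- Conservatism needs a positive within-pair correlation, and none is reported. The link between enrollment in a 2014 gambling portal and uptake of this app is plausible but is not shown. At ρ = 0 the unadjusted organization-level test has size 0.050.
- The direction depends on the organization-level term. Section 9 speaks of clustering by organization, yet the random effects it describes are at site level and optional. With site effects only, simulated type I error was 0.100 when the organization carries 25% of site-mean variance and pairs explain none of it. It was 0.063 when pairs explain half of that share, and 0.114 when the organization carries 50% and pairs explain a quarter of it. Such a test is anti-conservative even though the pairing is ignored.
- Leaving out pair terms is not always a loss. With site as the only level of clustering, pairing brings a clear advantage only at high correlation.

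Section 8 also mixes stratified, matched-pair and urn wording. A permutation test that swaps arms within pairs is exact only if assignment was independent in each pair.

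All of this stands. It limits the claim about direction and rules out an unqualified pair term. It does not answer the central point: under any of the three schemes the traits governed allocation, they are already held, and the models do not use them. One covariate avoids the degrees-of-freedom problem, and the organization random effect deals with the second reason above.

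**Conclusion.** The mismatch between design and analysis is established from the text. Its consequence is conditional. If the traits predict uptake and the test is made at organization level, omitting them gives a real type I error of about 0.03 to 0.01 for 20% to 50% shared variance, and power below what the design could deliver. If they do not predict uptake, little changes.

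The ρ range and the equal ICC split are assumptions. The trait-adjusted gains are a best case, because one trait is taken to carry all the shared variance; a score that carries only part of it would recover only part of the gain.

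A reader might also conclude that the stated power of .90 is wrong. This point does not show that: the figure follows from its own inputs. The change should be made, but the omission does not invalidate the comparison.

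**What to change.** In section 9:

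1. Pre-specify the innovation score as an organization-level covariate in the Reach, days-of-use and retention models.
2. Fit an organization random effect in each, and name the small-sample method for the arm test (13 df on organization means with one covariate).
3. In section 8, state which allocation scheme was actually used. If it was independent assignment within pairs, add a within-pair permutation test as a sensitivity analysis. Eight pairs give 2⁸ = 256 arrangements, so the smallest two-sided p-value is 2/256 = 0.008.
4. Do not make a pair term the primary adjustment unless its degrees-of-freedom method is stated.

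The cost is wording and one degree of freedom. The score is already obtained for matching, so no new data are needed. If it proves unpredictive, the loss is about 0.01 in power (0.65 against 0.66).
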